**Fig 5. Summary on TRLs metabolism**

**Fig 6. Study design**

### Kinetic modeling

Times series data from enrichments of plasma leucine, leucine in apo-B100 from VLDL1 and VLDL2, and glycerol from triglycerides from VLDL1 and VLDL2 are used as input to the kinetic model together with pool size measurements to simultaneously determine the kinetics of VLDL-triglycerides and apo-B100.

### Novelty and importance

This study provides a multidisciplinary *state-of-the-art* program to elucidate the deleterious effects of fructose on metabolism using a novel multidisciplinary approach in which clinical studies and molecular medicine are combined. The participating investigators, who all are at the scientific forefront in their respective fields, have different but highly complementary knowledge and technical competence. This enables us to perform innovative and cutting-edge science to dissect how fructose influences dyslipidemia, insulin resistance and inflammation utilizing novel imaging technology, lipidomics and genomics. The study focuses on abdominally obese subjects with hypertriglyceridemia to furthering evidence that these individuals are not only prone to type 2 diabetes but also to the development of related cardiometabolic abnormalities. The study is therefore designed to identify fructose mediated effects that are independent of weight gain. Overall, this research program has relevance to our understanding of factors involved in the development of type 2 diabetes and related metabolic complications including CVD risk factors.

Lipoprotein metabolism is a complex system in which abnormal concentrations of various lipoprotein particles can result from alterations in their rates of production, conversion and/or catabolism. Traditional methods that measure plasma lipoprotein concentrations only provide static estimates of lipoprotein metabolism and hence limited mechanistic information. By contrast, we will use tracers labeled with stable isotopes, which provide us with a powerful and cutting-edge tool for probing lipid and lipoprotein kinetics *in vivo* and furthering our understanding of the pathogenesis of dyslipoproteinemia. Thus, the combination of stable isotopes, studies of postprandial lipid metabolism and measurements of hepatic DNL will for the first time allow us to explore the dynamic changes leading to both postprandial accumulation of chylomicrons and elevated VLDL secretion. The great synergism and excellence of the network guarantees success of the proposed study.

***The microvesicles measured in urine samples are rapidly emerging as valuable, non-invasive ways to identify biomarkers of kidney metabolism. Consumption of fructose leads to increasing urate concentrations in plasma. The measurement of urine microvesicles offers a unique opportunity to study the effect of fructose consumption on novel biomarkers of kidney metabolism.***

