### **Objectives**

This project focuses on the deleterious effects of fructose-containing beverages on lipid metabolism. Our hypothesis is that consumption of fructose-containing beverages increases *de novo* lipogenesis (DNL) with numerous consequences on lipid and glucose metabolism, insulin resistance, inflammation and blood pressure. We further propose that fructose also decreases the removal of triglyceride-rich lipoproteins (TRLs) from the circulation by inhibiting the activity of lipoprotein lipase (LPL), a key enzyme in lipoprotein metabolism. We therefore focus our study on the effects of fructose on postprandial lipemia and features of ectopic fat deposition including visceral adipose tissue and liver fat content which are key features of individuals with metabolic syndrome and type 2 diabetes. So far, little data exist on the pathophysiological responses to fructose-containing beverages in obese subjects with multiple cardiometabolic risk factors. We will test the hypothesis that hypertriglyceridemic (HTG) obese subjects are particularly prone to the deleterious effects of fructose-containing beverages compared to normolipidemic (NTG) obese subjects. We have therefore designed our study to differentiate the weight-dependent vs. weight-independent effects of fructose-rich diet in HTG and NTG obese subjects.

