**This project addresses the following specific questions:**

1. Does a diet supplemented with fructose-containing beverages increase postprandial lipemia independently of body weight gain due to extra calories?
2. Does a diet supplemented with fructose-containing beverages increase DNL, VLDL production and liver fat deposition more in high risk HTG obese subjects than in NTG obese individuals?
3. Is the clearance of TRLs in the postprandial state impaired in response to a diet supplemented with fructose containing beverages?
  - A. Is a potential clearance defect of TRLs linked to responses of apo-CIII and apo-A5 to a diet with high fructose?
  - B. Are LPL mass and activity responses different in NTG vs. HTG subjects during fructose diet?
4. Is blood pressure raised by a diet supplemented with fructose-containing beverages?
5. Is the acute inflammatory response to a fructose-rich diet measured in the fasting state or the postprandial period exacerbated in obese subjects with HTG?
6. Do common variants in genes affecting lipid metabolism (individually and/or when combined) modify the effect of a diet enriched in fructose-containing beverages on lipid metabolism (in particular hypertriglyceridemia), and gene expression in adipose tissue?
7. Is gut microbiota modified by a diet enriched in fructose-containing beverages and are these changes linked to metabolic dysfunction?

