**Experimental diets**

Subject eligible for the study **will be randomly assigned to one of the two diet groups for 12 weeks:**

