**A) "Hypercaloric fructose diet group"**

Subjects will be instructed to drink 990 ml of a beverage sweetened with 7.6 % fructose per day while consuming a self-selected *ad libitum* (usual) diet. No advice is given to reduce the energy content of their usual diet. Subjects will be in positive energy balance and therefore subjected to a weight gain of up to 2.5 kg in the 3 month study period. The subjects will be followed by the trained dietitian 6 weeks after the study to ensure that the subjects return to a BW of maximum 1 kg above their baseline BW.

i Helsinki University plans to perform a kinetic study as an extension of the main study. The aim of the substudy is to elucidate the effects of fructose diet on lipoprotein metabolism using stable isotopes. This substudy replaces study visit 3 and is described on page 9.

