### **B) "Isocaloric fructose diet group"**

Subjects will be instructed to drink 990 ml of a beverage sweetened with 7.6 % fructose per day while consuming an isocaloric diet. This group will be instructed by a trained dietitian to reduce their carbohydrate intake from other source by 75 g in order to remain in neutral energy balance. Subjects are required to keep their weight stable during the 3 months and their daily energy intake will be adjusted by the dietitian if the body weight deviates more than 1 kg at the weekly check-ups.

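### The protocol says its design identifies fructose effects independent of weight gain, but both randomised arms drink the same fructose, so that effect rests on an uncontrolled before-after change in the isocaloric arm

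*Protocol*

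**What the plan says.** The claim appears in two places in the protocol, and one specific question depends on it.

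- Objectives: "We have therefore designed our study to differentiate the weight-dependent vs. weight-independent effects of fructose-rich diet in HTG and NTG obese subjects".
- Novelty and importance: "The study is therefore designed to identify fructose mediated effects that are independent of weight gain".
- Specific question 1 asks whether the fructose diet will "increase postprandial lipemia independently of body weight gain due to extra calories".

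Under Experimental diets, eligible subjects "will be randomly assigned to one of the two diet groups for 12 weeks".

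- Arm A, hypercaloric: "Subjects will be instructed to drink 990 ml of a beverage sweetened with 7.6 % fructose per day", on top of an unrestricted usual diet. "Subjects will be in positive energy balance and therefore subjected to a weight gain of up to 2.5 kg" over the study period.
- Arm B, isocaloric: "Subjects will be instructed to drink 990 ml of a beverage sweetened with 7.6 % fructose per day while consuming an isocaloric diet". A dietitian has these subjects cut other carbohydrate by 75 g and adjusts energy intake if weight moves by more than 1 kg.

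No glucose, placebo-beverage or usual-diet arm is described, and no crossover. The main measurements are taken before the diet and at its end. Under Power calculations, the first primary endpoint compares normotriglyceridemic (NTG) with hypertriglyceridemic (HTG) subjects. The second compares the isocaloric with the hypercaloric diet in HTG subjects.

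**The concern.** A randomised comparison can isolate only what differs between the arms, and the fructose beverage does not differ. The design property named in the Objectives and in Novelty and importance is therefore not one that the randomisation supplies.

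Two misreadings could follow. A rise in triglyceride AUC in the isocaloric arm could be reported as caused by fructose, on the strength of a study described as randomised. A null difference between arms could be read as showing that fructose does nothing, although both arms took it. The protocol itself, in the section on high fructose feeding and DNL, says that earlier liver-fat evidence could not tell calorie excess from fructose, so it matters which of the two the randomised contrast addresses.

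**Working it through.** **1. Exposure by arm.** Inputs: the arm A and arm B descriptions. Fructose per day is 990 × 0.076 = 75.2 in each arm, about 75 g. The randomised difference is 75.2 − 75.2 = 0 g/day. (The Dietary protocol section assigns 75 g to 750 ml, whereas 750 × 0.076 = 57. The passages must be reconciled, but the beverage is common to both arms either way.)

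**2. What each comparison estimates.** Let S be the effect of replacing other carbohydrate with fructose at stable weight, E everything that arm A's diet adds relative to arm B's, and d any change over 12 weeks not due to diet, taken as equal in both arms.

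- Arm B change = S + d
- Arm A change = S + E + d
- A minus B = E

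E bundles extra energy, weight gain, 75 g/day of other carbohydrate and the absence of dietitian restriction. S does not appear in A minus B. It appears only in arm B's change, together with d. If triglyceride AUC rose by 3.5 in both arms, A minus B would be 3.5 − 3.5 = 0 whatever the fructose effect.

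**3. The NTG versus HTG comparison.** A drift common to the two phenotypes cancels here. But phenotype is not randomised, both groups drink fructose, and the result is a difference in response between phenotypes. It does not isolate S.

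**4. The plan's own sample sizes.** Inputs from Power calculations: difference 3.5, SD 4.3, alpha 0.05 (two-sided assumed), power 0.80. The standardised difference is 3.5/4.3 = 0.814.

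- Unpaired, normal approximation: 2 × (1.960 + 0.842)² / 0.814² = 23.7, so 24 per group. The noncentral t gives 24.7, so 25, as stated.
- Paired, with 4.3 as the SD of the change: the noncentral t gives 13.9, so 14. The stated 15 gives 83.4 % power.

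The stated numbers reproduce, so the point rests on the arm definitions and not on a sample-size error.

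**5. Illustration of drift.** The documents give no figure for d, so these values are assumed. As a share of the 3.5 target: 0.5/3.5 = 14 % and 1.0/3.5 = 29 %. With no true fructose effect and an SD of change of 4.3, a paired test at nominal 5 % would reject as follows:

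| Assumed drift (mmol/l×hrs) | n = 15 | n = 64 |
|---|---|---|
| 0.5 | 7 % | 15 % |
| 1.0 | 13 % | 45 % |
| 2.0 | 39 % | 96 % |

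The n = 64 column takes half of the 128 subjects, assuming equal allocation, which is not stated. More subjects do not reduce the bias.

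**The case against.** The strongest reply is that the protocol never says randomisation identifies the fructose effect. It says the study is designed to separate weight-dependent from weight-independent effects. Arm B holds weight stable, arm A lets it rise, and both are measured before and after. Power calculations openly plans a paired test within a group. Stable weight before entry, lipid drugs stopped at least a month before screening, repeated food records with a pedometer, an activity questionnaire and weekly weight checks all limit some sources of change.

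Much of this stands. A reader might infer that the protocol claims randomised protection for the fructose effect, or that the design says nothing about it. The text supports neither: no sentence makes that claim, and arm B does remove weight gain as an explanation. A reader might also extend the point to questions 3, 4 and 7, but those do not mention weight. Nor do the arms differ in energy alone.

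What does not stand is that these safeguards replace a concurrent comparator. They monitor diet, activity and weight but do not address time, participation or regression to the mean. On one reading the protocol builds in an example. Diabetes is excluded by an oral glucose tolerance test, and the section on that test places it at screening and at the end of the diet. The selecting test would then also be the baseline, and excluding high values on it would tend to produce a later rise with no fructose effect.

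It is also fair that an assumed drift of 1.0 is below one standard error at n = 15 (4.3/√15 = 1.11). At n = 64 the standard error is 4.3/8 = 0.54, and the same drift is nearly two of them.

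**Conclusion.** The point holds in a limited form. The Objectives and Novelty and importance attribute to the design an ability to identify weight-independent fructose effects, and question 1 depends on it, but the randomised contrast does not carry that ability. It estimates the effect of the unrestricted hypercaloric diet against the energy-compensated diet at a fixed fructose intake. The weight-independent effect rests on arm B's before-after change, which is controlled for weight but not for time, trial participation, dietitian contact or regression to the mean.

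The conclusion follows from the arm definitions and needs no numerical assumption. The size of the bias is unknown, and the 14 to 29 % range is only an illustration. That shared changes cancel in A minus B assumes they are equal in the two arms, which dietitian contact may not be. A reader might infer that the trial must add an arm or cannot answer question 1 at all. The documents do not support going that far: the before-after change remains informative if it is described as what it is.

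**What to change.** Reword the Objectives, Novelty and importance, and question 1 to state three things:

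- The randomised A-minus-B comparison estimates the effect of the unrestricted hypercaloric diet versus the energy-compensated diet (extra energy and weight gain, bundled with 75 g/day of other carbohydrate and dietitian restriction) at the same fructose intake.
- Arm B's change at stable weight is an uncontrolled within-arm change, to be reported without randomised or causal wording.
- A null A-minus-B difference is not evidence of no fructose effect.

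Questions 3, 4 and 7 need only a note that changes on the fructose diet are uncontrolled.

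No arm, endpoint, visit or sample size changes. The cost is wording and a less favourable claim.
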